Complications of pre-eclampsia can affect both the mother and the fetus. Acutely, pre-eclampsia can be complicated by eclampsia , the development of HELLP

Syndrome , hemorrhagic or ischemic stroke, liver damage and dysfunction, acute kidney injury and Acute Respiratory Distress Syndrome (ARDS) (7)(8).

So early detection of pre-eclampsia and prevention of the occurrence of any of its complications would save the lives of many women and prevent the possible devastating maternal and neonatal outcome of pre-eclampsia, That's why we are concerned in our study with pre-eclampsia, covering the gestational age from 28 – 36 weeks (6) (9).

Mild pre-eclampsia represents 75% of cases with pre-eclampsia, possible progression to severe pre-eclampsia makes mild pre-eclampsia a serious problem that requires attention (10).

Previous studies have shown that expectant and conservative management of pre-eclampsia in the context of extreme prematurity may improve perinatal outcomes (11–13). Indeed, it has been estimated that for each additional day of pregnancy prolongation between 24 and 32 weeks of gestation, there is a nonlinear corresponding gain of 1% in fetal survival (14).

Sildenafil citrate has been used for increasing utero-placental perfusion in cases with intrauterine growth restriction, which makes it a promising drug in management of mild pre-eclampsia (15).

Its action is similar to the action of nitric oxide, which is a potent vasodilator, especially for the venules, besides being an inhibitor of platelet aggregation (16). During pregnancy, nitric oxide is synthesized in utero-placental tissues and endothelial cells, helping to maintain low vascular resistance in the utero- and fetoplacental circulations (17-19). Phosphodiesterase metabolizes cyclic guanosine monophosphate; therefore, phosphodiesterase type 5 inhibition leads to cyclic guanosine monophosphate increase with associated vasodilation, independently of nitric oxide. Therefore, phosphodiesterase type 5 inhibitors have the potential to achieve similar therapeutic goals when compared with nitric oxide.

A potential advantage of phosphodiesterase type 5 inhibitors is that they may overcome the main limitation to nitric oxide use in pregnancy, which is tolerance and headaches. The most studied phosphodiesterase type 5 inhibitor is sildenafil citrate,

which has previously shown promising outcomes both in vitro (20) and in animal studies (21) (22).

That is why we decided to study the role of Sildenafil Citrate in expectant and conservative management of mild pre-eclampsia, as it has shown its ability to be beneficial to both the mother and the fetus through increasing the maternofetal circulation perfusion and achieving a maternal hemodynamic stability (23) and compare it to the current NICE (National Institute for Health and Care Excellence) guidelines that are currently used, that recommends conservative management of mild pre-eclampsia through control of maternal blood pressure and frequent screening of maternal laboratory investigations' abnormalities to detect possible progression to severe pre-eclamptic toxemia (NICE guidelines 2010 [CG107]).

Aim of the work

- Aim of our study is to investigate if the use of sildenafil citrate in cases with mild pre-eclampsia is useful in pregnancy prolongation through prevention of its progression to severe pre-eclampsia and improved maternal and perinatal outcomes or not.

Subjects and methods

Study design

- Double blinded, randomized, placebo-controlled trial.

Settings and locations

- Obstetrics and Gynecology Department, Woman Health Hospital, Assiut University, Egypt.

Eligible Participants:

Inclusion criteria

- 1- Uncomplicated mild pre-eclampsia; No clinical or investigatory findings suggestive severe pre-eclamptic toxemia.
- 2- Gestational age of 28 – 36 weeks by good dates according to ACOG's – committee on obstetric practice – Method for Estimating Due Date (2014) who will receive the study's drug for at least one week before termination. (23)
- 3- Singleton viable pregnancy.
- 4- Age: 18-35 years.

Exclusion criteria

- 1- Severe pre-eclamptic toxemia (according to the NICE guidelines (2010): Hypertension in pregnancy: diagnosis and management)
- 2- Intrauterine growth retardation (23) (24).
- 3- Use of medication that could interact with sildenafil citrate such as nitrates erythromycin, ketoconazole, itraconazole, antiretroviral agents and others.
- 4- Presence of maternal co-morbidity disease as: DM, chronic hypertension, congestive heart failure, chronic kidney disease and SLE.
- 5- Placenta previa.
- 6- The patient is using aspirin.
- 7- The presence of a contraindication to the use of sildenafil citrate:
 - Hypersensitivity to sildenafil citrate or any of the tablet ingredients.
 - Patients with severe cardiovascular disease such as established cardiac failure and unstable angina pectoris.
 - Previous episode of non-arteritic anterior ischaemic optic neuropathy.
 - Severe hepatic impairment.
 - Hypotension (blood pressure <90/50 mmHg).
 - Hypertension (blood pressure >170/110 mmHg).
 - Recent history of stroke or myocardial infarction.

- Known hereditary degenerative retinal disorders such as retinitis pigmentosa.

Sample size

- Alpha error of 5%
- Power of study 95%
- Sample size: 80 patients who meet the criteria of the study would be randomized into the two groups (intervention and control group) with 40 patients in each group, in the Obstetrics and Gynecology Department, Woman Health Hospital, Assiut University, Egypt.

Interventions

Preliminary assessment of patient

- The patient will be admitted to the department of obstetrics and gynecology in Assiut University and will undergo the following:
 - Evaluation of vital signs of patient:
 - Pulse: Regular and the rate is between 60-100 beat/minute by palpating the radial artery.
 - Blood pressure: Maternal blood pressure would be measured as recommended by the NICE in the "Antenatal care" (2008):

Blood pressure should be measured as outlined below:

- The patient would sit with her left arm stretched.
- Remove tight clothing, ensure arm is relaxed and supported at heart level.
- Use cuff of appropriate size.
- Inflate cuff to 20–30 mmHg above palpated systolic blood pressure.
- Lower column slowly, by 2 mmHg per second or per beat.
- Read blood pressure to the nearest 2 mmHg
- Measure diastolic blood pressure as disappearance of sounds (phase V).

- Temperature: axillary temperature measurement using medical thermometer with range from 36° to 37°.
- Weight & height: to calculate the patient's BMI by dividing the patient's weight in kg by square her height in meters (kg/m^2).
- Ultrasound assessment: (Using the Medison SonoAce R5® ultrasound system)
- Fetal viability.
- Placental site.
- Fetal biometry: Biparietal diameter, Femur length, Abdominal circumference (using Hadlock formulas).
- Amniotic fluid index measured by the 4 quadrant view: more than or equal to 5 cm (ACOG guidelines on antepartum fetal surveillance (2014)).
- Doppler ultrasound assessment of the uterine, umbilical, aortic and middle cerebral arteries (Using the Medison SonoAce X8® ultrasound system): pulsatility (PI) and resistance (RI) indices and systolic/diastolic velocity (S/D) ratio, whatever suitable in each case condition by a well-qualified sonographer according to the standards of the ISUOG (2013).
- Investigations:
 - Complete blood count: Hemoglobin level, white blood cells' count, platelets' count and blood film.
 - Coagulation profile: Prothrombin time and concentration and INR.
 - Screening for gestational DM.
 - Kidney function tests: Blood urea and serum Creatinine.
 - Serum uric acid.
 - Liver function tests: AST, ALT, serum bilirubin (total, direct and indirect), serum total protein and albumin.
 - Urine analysis and 24- hour's urine collection for: 24-hours protein collection in urine, urine output in 24-hours and creatinine clearance.

Randomization

- The patients will randomly allocated to either the control group or intervention group using computer generated random number tables and opaque sealed envelopes containing the patients' group allocation. The envelopes will be prepared and sent to an assigned nurse, who opens each envelope when a patient – who meets the criteria of the study- comes. All patients will be blinded to the allocation to avoid bias.
- The patients will be divided into a red group and a blue group where the intervention group would not be known by the clinician. (double-blinded)
- The intervention group will be supplied with Sildenafil Citrate (Respasio® 20mg tablets manufactured by Pharma Right Group , Egypt) according to the patient's weight by the rate of (1.5 mg/kg/day) divided into three doses per day (every 8 hours) (25-28). While the control group will be supplied with a placebo drug that has the same shape, size and color but without the active ingredient and it would also be taken in a similar way. The placebo tablet will be manufactured at the faculty of pharmacy, Assiut University.
- The patients of each group would stay in the hospital for 48 hours after the beginning of the medication for blood pressure monitoring (4 times per day) and to record any side effects detected from the medication taken.

Follow up visits:

- 1) The patients would be followed up at the obstetric outpatient clinic every 2 weeks till delivery. (According to the NICE guidelines “Hypertension in pregnancy” (2010) and the NICE guidelines “Antenatal care” (2008))

2) The follow up visits will include:

- Blood pressure measurement and review the patient's blood pressure measurements in the past 2 weeks (the blood pressure would be measured 3 times a week in any easily accessible facility to the patient).
- Urine dipstick analysis.
- Complete blood count.
- Serum creatinine & blood urea.
- AST & ALT.
- Serum uric acid.
- Obstetric ultrasound and doppler ultrasound.

- Compliance to treatment will be ensured by checking the remainder of the medication strip.

Termination of pregnancy:

- If the patient developed any sign or investigatory/laboratory finding that represent severe pre-eclamptic toxemia:
 - 1) Persistent elevated blood pressure more than 160/110 mmHg.
 - 2) HELLP syndrome.
 - 3) Eclampsia.
 - 4) Intrauterine fetal death.
 - 5) Abrupt body swelling.
 - 6) Severe headache, epigastric pain and/or right hypochondrial tenderness.
 - 7) Elevated liver enzymes: ALT or AST rising to above 70 iu/litre.
 - 8) Platelet count falling to below 100×10^9 per litre.

9) Serum creatinine >125 mmol/litre (29).

- If no complications occurred and the maternal blood pressure is controlled on the medication , termination would be after completion of 36 weeks and 6 days as recommended by the NICE guidelines (2010) : “Hypertension in pregnancy : Diagnosis and management”

Primary outcome

Gestational age at time of termination and maternal outcome in terms of whether the disease would progress to severe pre-eclampsia or not.

[figure not shown]
Secondary outcomes

- 1- Neonatal outcome in terms of survival and neonatal well-being (by obtaining the birth weight and the apgar score at 1 and 5 minutes and direct postnatal need to NICU).
- 2- Control of maternal blood pressure.
- 3- Method of termination of pregnancy.
- 4- Identification of possible maternal side effects from the use of sildenafil citrate i.e.; headache, flushing and dyspepsia.
- 5- Evaluation of the effect of sildenafil citrate on the feto-maternal circulation through the Doppler ultrasound.

Final status:

- We will specify the number of patients who were candidates for the study ,the number of patients who were excluded for not meeting the criteria ,the number of patients who were included the study, the number of patients who were excluded for lack compliance to treatment or dropped follow-up visits and the number of patients who successfully completed the study till delivery.

THE TRIAL FLOW CHART

Approval of Ethical Considerations

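### The plan lets the sonographer choose among PI, RI and S/D case by case and never names the Doppler outcome, so the Doppler comparison can rest on mixed or selectively recorded indices

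*Combined protocol and SAP*

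**What the plan says.** In the combined protocol and SAP, under Interventions, Preliminary assessment of patient, the plan calls for "Doppler ultrasound assessment of the uterine, umbilical, aortic and middle cerebral arteries". The measures are PI, RI and the S/D ratio, "whatever suitable in each case condition by a well-qualified sonographer". The sentence closes by citing the ISUOG 2013 standards, without stating which index they call for.

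Under Follow up visits, women are to be "followed up at the obstetric outpatient clinic every 2 weeks till delivery", and the scan at those visits is described only as "Obstetric ultrasound and doppler ultrasound".

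Item 5 under Secondary outcomes is "Evaluation of the effect of sildenafil citrate on the feto-maternal circulation through the Doppler ultrasound". It gives no index, vessel, time point or change measure. The Statistical Analysis section offers t-tests and chi-square tests at 0.05, with nothing specific to Doppler and no multiplicity rule.

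**The concern.** The phrase about suitability ties what is recorded to the condition of the individual woman. Three things can follow.

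- **Scale.** PI, RI and S/D are on different scales, so raw values of different indices cannot be averaged or compared by a t-test.
- **Selection.** If each index is analysed only where it was recorded, the women contributing to it are a subset chosen by their condition, not the randomised group.
- **Change over time.** Nothing requires the same index at baseline and follow-up in the same woman, so a within-woman change or a baseline adjustment may be impossible.

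A second and separate weakness is that the outcome is unnamed. Even with complete recording, the vessel and index to be reported could be chosen after the results are seen. What is at stake is the trial's reading on feto-maternal circulation, which the introduction presents as the way the drug would work.

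**Working it through.** **Plan's own figure.** The plan gives no figure for Doppler. Its only design figure is 80 women, 40 per arm, at 5% alpha and 95% power (Sample size). It states no effect size or SD, so the number cannot be reproduced. It can be solved backwards. With a two-sided test (assumed) and the normal approximation, d = (1.960 + 1.645) × √(2/40) = 0.806. This serves below only as an illustrative effect size.

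**1. Are the indices interchangeable?** By definition RI = (S − D)/S = 1 − 1/(S/D). An S/D of 2.5 is therefore an RI of 0.60, and each can be computed from the other. PI also uses the mean velocity over the cycle, so neither RI nor S/D yields it. When end-diastolic velocity is zero, S/D has no value.

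**2. Pooling raw values.** A simulated t-test assumed S/D with mean 2.8, SD 0.4, d = 0.806 and 40 per arm.

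| Share recorded as RI | Power |
|---|---|
| 0% | about 95% |
| 25% | about 22% |
| 50% | about 12% |
| 100% | about 93% |

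The loss comes from mixing the scales, not from using RI. For RI and S/D it is avoidable by conversion. For PI it is not.

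**3. Analysing each index only where recorded.** The standard error of a difference in means is σ√(2/n) with n per arm.

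- n = 40: 0.224σ
- n = 20: 0.316σ
- Ratio: √2 = 1.41, a rise of 41%

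Power is Φ(d√(n/2) − 1.96):

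| Women per arm with the index | d = 0.806 | d = 0.5 |
|---|---|---|
| 40 (everyone) | 95% | 61% |
| 20 (even split over two indices) | 72% | 35% |
| 13 (even split over three) | 54% | 25% |

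The splits and effect sizes are assumptions. The table shows loss of precision only. Selection bias would come on top and cannot be sized from the documents.

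**4. Unnamed outcome.** Four arteries × three indices = 12 possible comparisons at one time point. If the tests were independent, the chance of at least one false positive would be:

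- 12 tests: 1 − 0.95¹² = 0.46
- 8 tests (RI and S/D counted as one, so 4 × 2): 1 − 0.95⁸ = 0.34

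The measures come from the same women and often the same waveform, so positive correlation will bring both figures down.

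**The case against.** The strongest reply is that the list of indices is joined by a plain conjunction. A sonographer who records all three for every woman complies with the text, and the suitability phrase might concern which vessels are examined. That stands: mixing is permitted, not certain. A reader might infer that the Doppler comparison will be made on mixed indices, and the documents do not support that.

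The clause also sits in the preliminary assessment, before randomisation, so the choice of index at that scan cannot depend on treatment. The plan also keeps group identity from the clinician. A reader might infer bias between arms, and the documents do not establish it. The reassurance is partial, however. Follow-up Doppler has no specification of its own, so the baseline wording is the only guide to practice. The sonographer is not named in the blinding text. If treatment changes the waveform, a choice driven by the woman's condition after randomisation could differ by arm even with a blinded operator.

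The ISUOG reference may narrow the choice in practice. The protocol does not say that it does, and it keeps the case-by-case wording beside the citation.

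Two further limits are accepted. Convertibility of RI and S/D removes part of the scale problem, though not where PI is involved. The 46% comes from the unnamed outcome and would exist even if every index were recorded in everyone. A reader might attribute it to the sonographer's discretion, which would be wrong.

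**Conclusion.** The concern holds in this limited form. The plan contains a discretionary rule for the Doppler index at baseline, gives no rule at follow-up, and names no measure for secondary outcome 5. Followed as written, it can produce values that are not comparable between women or within a woman, or that come from a condition-dependent subset.

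The size depends on practice that the documents do not describe. A 41% larger standard error needs the index to be missing in half the women. The power figures need the assumed effect sizes and even splits. The false-positive figures of 46% and 34% assume independence and that all the comparisons are tested.

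It might be inferred that the trial's main conclusions are at risk. They are not: gestational age at termination and progression to severe disease do not use Doppler, and Doppler is the last of five secondary outcomes. The change should still be made before recruitment, because a PI that was never recorded may not be recoverable later.

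**What to change.** - Delete the phrase that leaves the index to suitability in each case.
- Record PI, RI and S/D from the same waveform for each vessel examined. Enter S/D as not calculable when end-diastolic flow is absent.
- Require at least the uterine and umbilical arteries at baseline and at the follow-up Doppler scans already planned. The other vessels need not be added at follow-up.
- Name one index (for example PI) in the uterine and umbilical arteries as the Doppler outcome. Compare arms at one fixed time point, for example the first 2-week visit, adjusting for the baseline value.
- Report all other vessels, indices and visits descriptively.

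One point to settle when choosing the time point is that some women may deliver before it. Entry runs to 36 weeks and planned termination follows 36 weeks 6 days. Subtracting 14 days gives 34 weeks 6 days, so a woman entering later than this may have no 2-week scan. The plan should say how such women are counted and report their number by arm.

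The cost is protocol wording and a fixed table on the case report form. The three values come from one waveform. Scanning time rises only if the uterine and umbilical arteries would not otherwise have been examined at follow-up. The sonographer loses some freedom, and the trial gives up significance claims on the other vessels and indices.

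### Entry gestational age is tied to both primary outcomes but is used neither in the allocation nor in the analysis; adjusting for it is a free improvement, and the route to 40 per group should be stated.

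*Combined protocol and SAP*

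**What the plan says.** All references are to the combined protocol and SAP.

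- **Sample size:** 80 women, "randomized into the two groups (intervention and control group) with 40 patients in each group", at alpha 5% and power 95%. No effect size, SD or event rate is given.
- **Randomization:** on the sequence: "The patients will randomly allocated to either the control group or intervention group using computer generated random number tables and opaque sealed envelopes". On implementation: "The envelopes will be prepared and sent to an assigned nurse, who opens each envelope when a patient" who meets the criteria arrives. No block, fixed-total rule, stratum or minimisation is mentioned.
- **Inclusion criteria, item 2:** "Gestational age of 28 – 36 weeks by good dates".
- **Termination of pregnancy:** without complications and with blood pressure controlled, pregnancy ends after 36 weeks and 6 days are completed; signs of severe disease lead to earlier termination.
- **Primary outcome:** gestational age at termination, and whether the disease progresses to severe pre-eclampsia.
- **Statistical Analysis:** t-test and chi-square at the 0.05 level. No baseline covariate is named.

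**The concern.** Entry gestational age is linked to both primary outcomes by the design itself. A woman who enters at 35 weeks 0 days cannot have a termination at 31 weeks, and she has 1 week 6 days at risk before the planned end at 36 weeks 6 days. A woman who enters at 28 weeks 0 days has 8 weeks 6 days. The variable is known before allocation and costs nothing to record, yet the plan leaves it out of both the sequence and the tests.

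At stake is precision. Variation in entry age stays in the error term of the unadjusted tests. If the arms also happen to differ in entry age, a reader of one 80-woman trial cannot easily tell how much of an observed difference in weeks or in progression comes from that. Separately, the plan fixes 40 per group without saying what mechanism delivers it.

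**Working it through.** **The plan's own figure.** The 40 per group cannot be reproduced, because no effect size is given. Back-solving at two-sided alpha 0.05 (sidedness is not stated) and power 95%: d = (1.960 + 1.645) × √(2/40) = 0.81 SD.

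**Group sizes, if allocation were simple.** P(exactly 40:40) = C(80,40)/2^80 = 8.9%. P(50:30 or worse) = 3.3%. At d = 0.81, power is 95.0% at 40:40 and 93.7% at 50:30, so uneven arms by themselves matter little.

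**Chance imbalance in entry age at 40:40.** SE of the difference in means = SD × √(2/40). The SD is an assumption; uniform entry over 28 to 36 weeks gives 8/√12 = 2.31 weeks.

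| Assumed SD (weeks) | SE (days) | P(gap > 5 days) | P(gap > 7 days) |
|---|---|---|---|
| 1.5 | 2.3 | 3% | 0.3% |
| 2.31 (uniform) | 3.6 | 17% | 5% |
| 2.5 | 3.9 | 20% | 7% |

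**What different lists do to that gap** (20,000 simulated trials, uniform entry):

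| Scheme | SD of difference in mean entry age (weeks) |
|---|---|
| Simple randomisation | 0.521 |
| Fixed 40 + 40 list | 0.516 |
| Blocks of 4, no strata | 0.517 |
| Blocks of 4, stratified at 32 weeks | 0.265 |

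Restriction alone leaves the gap where it was. Stratification about halves it (3.6 to 1.9 days), and a gap above 5 days falls from 17% to under 1%.

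**Effect on gestational age at termination.** Assume uniform entry age e and a constant progression hazard h per week, with termination at progression or at 36w6d (36.86 weeks), whichever is earlier. Then E[Y | e] = e + (1 − exp(−h(36.86 − e)))/h.

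Hand check at h = 0.1: entry at 28 gives 28 + 5.88 = 33.88 weeks, and entry at 36 gives 36 + 0.82 = 36.82 weeks. The average slope is (36.82 − 33.88)/8 = 0.37. Simulated regression gives:

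| h per week | Progression by 36w6d | Slope on entry age | Shift from a 5-day gap | Variance explained |
|---|---|---|---|---|
| 0.03 | 13% | 0.13 | 0.7 day | 6% |
| 0.05 | 21% | 0.21 | 1.1 days | 10% |
| 0.1 | 37% | 0.38 | 1.9 days | 19% |
| 0.2 | 58% | 0.60 | 3.0 days | 34% |

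**Gain from adjustment.** The SE shrinks by a factor of about √(1 − R²): √0.94 = 0.97 to √0.66 = 0.81. In sample-size terms, 80 women analysed with adjustment are worth about 80/0.94 = 85 to 80/0.66 = 121 analysed without it.

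**The case against.** The strongest objection is that a reader might infer that allocation is unrestricted, and the documents do not say so. Random number tables are a source of randomness and can equally be used to shuffle a fixed set of 40 + 40 or to build blocks. Envelopes prepared in advance fit such a set, and the plan states "with 40 patients in each group". This stands: the documents are silent on restriction, which is a gap in description and no proof of simple randomisation. The 8.9% therefore applies only if allocation is simple. Likewise, no step that forces 40:40 at the end is described, so predictable last envelopes are a supposition.

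A second tempting reading is that missing blocks cause the entry-age imbalance. They do not: a fixed 40 + 40 list leaves it unchanged. Counts by stratum depend more on the scheme. A difference of six or more women below 32 weeks occurs in about 38% of trials under simple allocation but 22% at 40:40.

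A third is that imbalance would invalidate the result. Chance imbalance after randomisation is not bias, and the t-test's standard error already carries the entry-age variation; simulated type I error was 4.8 to 5.6% across hazards of 0.03 to 0.2. At hazards of 0.1 to 0.2, a 5-day gap moves the outcome by 2 to 3 days, which is less than one standard error of the arm difference (3.2 to 3.7 days).

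Finally, stratification is optional at a single site. That also stands. None of this answers the remaining point: a strong, pre-randomisation predictor is available and left out of the analysis.

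**Conclusion.** This is a free improvement, not a flaw that invalidates the trial. No restriction or stratification is described, so the route to 40 per group is unspecified, and entry gestational age is used in neither the allocation nor the analysis.

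The cost is precision and interpretability. Depending on assumptions, between a small share (6%) and a third (34%) of the variance in gestational age at termination is left unexplained when it need not be. An entry-age gap above one week is uncommon, at 0.3 to 7% of trials.

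The structural link between entry age and both outcomes follows from the documents. The sizes do not: they rest on an assumed entry-age SD of 1.5 to 2.5 weeks, uniform entry for the outcome model, and a constant hazard of 0.03 to 0.2 per week. At the low end of those ranges the gain is modest.

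**What to change.** **In Statistical Analysis:** pre-specify that both primary comparisons are adjusted for entry gestational age as a continuous covariate, with a linear model for gestational age at termination and a logistic model for progression, in place of the unadjusted t-test and chi-square. This uses data already collected and is available even if allocation has begun, provided it is written down before outcomes are seen by arm. Two points to note: the adjusted odds ratio is conditional on entry age, and at the low end of the assumed progression range there would be few events (13% of 80, about 10), so the plan should say what is done if the logistic model does not fit.

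**In Randomization:** state how the sequence is generated and how 40 per group is reached.

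**If allocation has not begun:** also generate the list in permuted blocks of random size, stratified by entry gestational age in two strata (for example below 32w0d, and 32w0d or later). Use separately numbered envelope series, keep the block sizes from the site, and include the stratum or continuous entry age in the analysis. The cost is a new list and two envelope series, and the nurse must pick the series by gestational age. Blocking without stratification would not reduce entry-age imbalance. If allocation is under way, leave the list alone and rely on adjustment.

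### Side-effect recording is provided for only in the first 48 hours, so as written outcome 4 describes early tolerability and leaves 71% to 97% of planned treatment days without symptom collection

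*Combined protocol and SAP*

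**What the plan says.** All references are to the combined protocol and SAP.

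- **Secondary outcomes, item 4:** "Identification of possible maternal side effects from the use of sildenafil citrate i.e.; headache, flushing and dyspepsia". No period and no method of collection are given.
- **Randomization, last bullet:** both groups stay in hospital for 48 hours after starting medication, "for blood pressure monitoring (4 times per day) and to record any side effects detected from the medication taken". No other available section provides for recording side effects.
- **Follow up visits:** patients attend every two weeks until delivery. The content is introduced by "The follow up visits will include" and then itemised: blood pressure, with review of readings taken three times a week; urine dipstick; blood count; creatinine and urea; AST and ALT; uric acid; obstetric and Doppler ultrasound. The list ends with a tablet check: "Compliance to treatment will be ensured by checking the remainder of the medication strip". It contains no symptom or side-effect question.
- **Termination of pregnancy:** without complications, delivery is planned after 36 weeks and 6 days, with the woman still on medication.

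**The concern.** The three named side effects are symptoms. Two of them, flushing and dyspepsia, would not show in any blood test, urine test or scan on the visit list, and neither would ordinary headache. Someone has to ask. The plan gives a specific occasion for recording them and a specific visit list that omits them, so a site following the text would collect them for two days and then stop, while dosing continues for weeks.

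Three things depend on this:

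- **What outcome 4 means.** With collection confined to the first 48 hours, it cannot describe symptoms that start later or persist under repeated dosing.
- **Why tablets are missed.** Final status counts women excluded for poor compliance. A woman who cuts back because of dyspepsia appears there through her leftover tablets, with no reason attached.
- **The rationale.** The introductory text presents tolerance and headache as the main limitation of nitric oxide that this drug class may overcome. Two days of recording says little about that over weeks of use.

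**Working it through.** The documents state no treatment duration, so there is no figure of the plan's own to reproduce. The exposure has to be derived.

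**Inputs**
- Recording window: 48 hours = 2 days (Randomization, last bullet).
- Entry: "Gestational age of 28 – 36 weeks by good dates" (Inclusion criteria, item 2).
- Shortest intended exposure: women "who will receive the study's drug for at least one week before termination" (same item), so 7 days.
- Planned end: after completion of 36w6d (Termination of pregnancy), read as 36w6d or 37w0d.
- Visit interval: 14 days (Follow up visits).

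**Step 1: share of exposure days inside the window**

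D = end minus entry, in days; covered share = 2/D.

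- Longest: (36×7 + 6) − 28×7 = 258 − 196 = 62 days, or 63 if counted to 37w0d.
- Entry at 32w0d, to 37w0d: 259 − 224 = 35 days.
- Entry at 34w0d, to 36w6d: 258 − 238 = 20 days.

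| Case | D (days) | Covered, 2/D | Outside window |
|---|---|---|---|
| 28w0d to 36w6d | 62 | 3.2% | 96.8% |
| 28w0d to 37w0d | 63 | 3.2% | 96.8% |
| 32w0d to 37w0d | 35 | 5.7% | 94.3% |
| 34w0d to 36w6d | 20 | 10.0% | 90.0% |
| One-week minimum | 7 | 28.6% | 71.4% |

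Most of the exposure therefore lies outside the window for every woman who meets the one-week minimum.

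**Step 2: days are not events**

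The documents give neither onset times nor rates. As an illustration only, assume a constant rate of first onset and a cumulative incidence p over D days. The share of first events falling in the first 2 days is then [1 − (1 − p)^(2/D)] / p.

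- D = 63: p = 10% gives 0.0033/0.10 = 3.3%; p = 50% gives 0.0218/0.50 = 4.4%.
- D = 7: p = 10% gives 0.0297/0.10 = 29.7%; p = 50% gives 0.1797/0.50 = 35.9%.

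If onset clusters around the first doses, 48 hours captures more than this, and possibly much more. The range is therefore open, and only the share of days is firm.

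**Step 3: would the existing visits be enough to close the gap?**

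The number of two-weekly visits before 37w0d is the whole part of (D − 1)/14, with D counted to 37w0d.

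| Entry | D (days) | Visits before 37w0d |
|---|---|---|
| 28w | 63 | 4 |
| 30w | 49 | 3 |
| 32w | 35 | 2 |
| 34w | 21 | 1 |
| 35w | 14 | 0 |
| 36w | 7 | 0 |

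Questions at visits alone would miss women entering at 35 or 36 weeks, so an assessment at delivery is also needed.

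**The case against.** The strongest reply is that this is silence, not a restriction. The Randomization bullet gives the purposes of the inpatient stay and does not say that recording ends at discharge. Outcome 4 has no window, follow-up runs to delivery, the flow chart is not shown in the copy reviewed, and a case-report form may contain the question. This stands as a limit: that recording happens only in the first 48 hours is inferred from omission. It does not remove the point, because a named recording occasion together with an itemised visit list that leaves symptoms out is what a site would follow.

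The visits are also not blind to safety. Blood pressure effects and liver-enzyme rises would be seen throughout, and leftover tablets reveal missed doses. Severe headache and epigastric pain are termination criteria, which can work only if such symptoms come to attention after discharge. All of this stands, and it narrows the gap to flushing, dyspepsia, non-severe headache and the reasons for missed tablets. A termination criterion counts a symptom as severe disease; it does not record it as a side effect.

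A reader might infer more than the documents support:

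- *That about 97% of side effects would be missed.* That figure is a share of days, for the longest exposure only. No onset data are given.
- *That 48-hour rates will be presented as tolerability of the whole course.* The protocol does not say how outcome 4 will be reported.
- *That the trial cannot meet its safety objective.* The Aim states no such objective. Side effects are one of five secondary outcomes, and early blinded recording in both arms can still identify some of them.
- *That no controlled evidence in pregnancy exists, because the labels in the Appendix say so.* The reference list itself cites two randomised trials of sildenafil for treating pre-eclampsia.

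**Conclusion.** The point holds in a limited form and should be acted on. The only side-effect recording that the protocol provides for covers 2 days of a planned exposure of about 7 to 62 days, which is 28.6% down to 3.2% of treatment days. Beyond that window the three symptoms named in outcome 4 have no listed collection.

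This rests on three assumptions: that dosing continues until delivery, as the tablet check at visits and the planned-delivery rule imply; that the written visit list is what sites will do; and that the woman meets the one-week minimum. Earlier delivery for severe disease shortens exposure and raises the covered share. How many events are lost cannot be estimated from the documents.

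**What to change.** - **Collection.** Use one short checklist during the 48-hour stay, at every existing two-weekly visit and at admission for delivery: headache, flushing, dyspepsia and any other complaint; onset date; and whether tablets were missed because of it. Ask it in the same words in both arms, by staff blinded to allocation.
- **Definition.** State outcome 4 as any occurrence from first dose to delivery, and report the 48-hour rate separately.
- **If later recording is already intended,** a sentence under Follow up visits and the window in outcome 4 are enough.

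The cost is small: a few questions at contacts already scheduled and one block on the case-report form. Recall over two weeks will be imperfect, and reported side-effect rates may be higher than a 48-hour figure. Treatment and clinical rules are unaffected.
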